Design	
The study is designed as an open-label, single arm cohort study, to evaluate the Acceptability, safety and Use of daily oral PrEP (FTC/TDF) in 150 adolescents (approximately 75 participants at each site), ages 15-19 years, their adherence to study product, and any changes in their sexual and health behaviors over a 12-month (52 week) period. All participants will complete an initial (12 week) 3- month period, during which they will receive PrEP as part of a combination prevention package. At all subsequent visits, participants will be offered the opportunity to hear real-time feedback of drug level data as part of their adherence counseling or they may choose to have adherence counseling without the feedback of drug level data. The decision about feedback as well as self reported adherence will be captured via interviewer administered questionnaires at each follow up visit. At the first 3 month (week 12) visit and 3 monthly (weeks 24, 36, 48) intervals thereafter participants will be offered the following options: full package + PrEP, stop PrEP and continue with rest of package or alternatively re-start PrEP if previously stopped. This will occur during protocol-specified study visits.
 
Participants will be followed regardless of PrEP usage for a total of 12 months (52 weeks). PrEP may be stopped at any other clinic visit but recommencement can only occur at a scheduled visit when all medical criteria are met including a negative HIV test. Adherence counselling will be offered at every visit with options to have drug level feedback or not as part of this counselling.

Study site	The study will be conducted at The Desmond Tutu HIV Foundation research site in Masiphumelele, Cape Town and the Perinatal HIV Research Unit (PHRU) site in Soweto, near Johannesburg.
Study drugs	FTC/TDF or Truvada® is a 200mg/300mg fixed dose combination tablet containing emtricitabine (FTC) and tenofovir disoproxil fumarate (TDF).
Study population	Healthy, HIV-uninfected adolescents, 15 and 19 years of age
Number of participants	150 enrolled participants (approximately 75 participants at each site)

Treatment Regimen	Participants will be provided with a supply of FTC/TDF tablets, taken orally, once daily for first 3 months. Thereafter, these tablets will only be supplied to those who indicate willingness to take PrEP and who do not have a clinical contraindication to do so.

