8.1 ADVERSE EVENT PROCEDURES AND REPORTING REQUIREMENTS

An Adverse Event (AE) is defined as any untoward medical occurrence in a study participant, from the time of enrollment through when s/he terminates from the study; it does not necessarily have a causal relationship with the study product. As such, an AE can be an unfavorable or unintended sign (including an abnormal laboratory finding, for example), symptom or disease temporally associated with the use of a study product, whether or not considered related to the product. This definition is applied to all participants beginning from the time of enrollment.

Study site staff will document in source documents and the appropriate AE Log CRF all AEs reported by or observed in enrolled study participants regardless of severity and presumed relationship to study product. The severity of clinical symptoms will be scored using the DAIDS Table for Grading the Severity of Adult and Pediatric AEs, Version 2.0 Dated Nov 2014. The Investigator or designee must determine the severity of the AE and document it on the appropriate CRF (AE Form). Each adverse event that the participant reports will be graded for severity according to the DAIDS grading scale. If not on the grading scale then the following scale will be applied:

- **Mild:** participant was able to perform all normal activities.
- **Moderate:** the participant had to discontinue some activities due to the adverse event.
- **Severe:** the participant was incapacitated by the adverse event and unable to perform normal activities.
- **Life-threatening** participant experienced extreme limitation in activity, significant assistance required; significant medical intervention / therapy required, hospitalisation or hospice - care probable.

An AE **does not** include:

- Pre-existing diseases or conditions present or detected prior to start of study intervention that do not worsen.

- Medical or surgical procedures (e.g. surgery, endoscopy, tooth extraction, transfusion); the condition that leads to the procedure is an adverse event.
- Situations where an untoward medical occurrence has not occurred (e.g. hospitalization for elective surgery, social and/or convenience admissions).

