All AEs will be captured regardless of the association or otherwise to the study intervention and reported on the AE CRF in accordance with study specific procedures. All AE reports will contain at least the date the AE occurred, a brief description of the event, the relationship to study intervention, the action taken, the outcome, date resolved, and the severity of the event.

Suspected, Unexpected Serious Adverse Reactions (SUSARS) will also be reported after the protocol-defined AE reporting period, if the study staff become aware of these at any time.

Requirements, definitions and methods for expedited reporting of Adverse Events (AEs) are outlined in Version 2.0 of the DAIDS EAE Manual, which is available on the RSC website at <http://rsc.tech-res.com/safetyandpharmacovigilance>.

The DAIDS Adverse Experience Reporting System (DAERS), an internet-based reporting system, must be used for expedited AE reporting to DAIDS. In the event of system outages or technical difficulties, expedited AEs may be submitted via the DAIDS EAE Form. For questions about DAERS, please contact DAIDS-ES at [contact]. Site queries may also be sent from within the DAERS application itself.

Where DAERS has not been implemented, sites will submit expedited AEs by documenting the information on the current DAIDS EAE Form. This form is available on the RSC website:

<http://rsc.tech-res.com/safetyandpharmacovigilance/>. For questions about expedited reporting, please contact DAIDS RSC [contact].

Designated study staff will submit AE information and any other relevant safety information to the local Ethics Committee(s) in accordance with EC requirements.

Reporting Requirements for this Study

- The SAE Reporting Category, as defined in Version 2.0 of the DAIDS EAE Manual, will be used for this study.
- The study agents for which expedited reporting are required are: Tenofovir and Emtricitabine as a single combined formulation known as TRUVADA.

- AEs and SAEs will be reported throughout the period of trial follow up.

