participants. Should the SMC or the PSRT detect evidence of harm such that the recommendation for halting or modifying the study is made, then this will be communicated to the PI, The protocol team and the DAIDS prevention division. The IRB and MCC will also be informed of the discontinuation of the study and/or the modification and reasons for modification of the study. All further enrollment, and study activities other than safety follow up will be put on hold. Participants, guardians and CABS will be notified as soon as possible after next steps are identified.

DATA ANALYSIS PLAN

A customized data entry and management system will be implemented for the project in Microsoft Access. Data will be analysed using the statistical programme STATA (Stata Corporation, College Station, Texas, USA). Simple descriptive statistics including frequency distributions will be used to assist in data cleaning and summarization.

The analysis plan for each of the study objectives (per 10.2 above) is detailed below. (Note that throughout the analysis, all statistical tests will be 2-sided using an alpha of 0.05.)

Endpoints:

A. PRIMARY

1. Primary: Use

Number of adolescents who continue to use PrEP after the initial 3 month period and the total time on PrEP for each adolescent and for the cohort as a whole.

Analysis:

Proportions of participants (a) willing to use and (b) taking up PrEP will be described with point estimates and exact 95% confidence intervals. “Remaining on PrEP” will be defined as any self-reported use of PrEP at each study interval (regardless of adherence) over the 9-month follow-up period, as a binary outcome. The first 3-month “use” will be 100% for all 150 participants. We will use product-limit methods to examine ‘survival’ proportions for

CHAMPS: Choices For Adolescent Prevention Methods for SOUTH AFRICA

Pilot study B: “PlusPills”

A Demonstration Open Label Study to Assess the Acceptability and Use of Truvada Pre-exposure Prophylaxis in Healthy, HIV-Uninfected Adolescents, 15-19 Years of Age.

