A Demonstration Open Label Study to Assess the Acceptability and Use of Truvada Pre-exposure Prophylaxis in Healthy, HIV-Uninfected Adolescents, 15-19 Years of Age.

sum tests, replaced by analysis of variance or u-tests for global comparisons across polytomous groupings.

3. Primary: Safety

Grades 2, 3, and 4 clinical and laboratory adverse events

Analysis:

This analysis will be based on descriptive statistics.

B. Secondary Endpoints:

1. Secondary: Adherence

Adherence to daily regimens of oral PrEP as evidenced by the use self-report, pill counts, and proportion of participants on FTC/TDF who have detectable drug levels.

Proportion of doses that are taken as instructed.

Proportion of blood samples with detectable drug levels

Proportion of adolescents with detectable drug levels who report using PrEP

Analysis Plan:

There are 3 different measures of PrEP adherence that will be used for the primary adherence endpoint: Participant self-report, pill count results, and detectable drug levels.

While the distributions of each of these measures may vary, a priori we anticipate that analysis of each of these 3 measures will use two different binary metrics from data at each study visit: (i) perfect adherence (defined as adherence data that do not suggest any missed doses, e.g., pill count data consistent with daily dosing, or no missed doses detected on self-report); and, (ii) effective adherence (defined as adherence levels that are consistent with protection against HIV exposure based on available data from PrEP efficacy trials, e.g., >85% doses taken, from pill count, or self-report; or therapeutic drug levels on biological assays).

Note that drug levels will be used in analyses of effective adherence only.

Analyses of adherence data will be based on the binary constructs of perfect and effective adherence as well as continuous measures of the proportion of PrEP doses taken; both the

CHAMPS: Choices For Adolescent Prevention Methods for SOUTH AFRICA

Pilot study B: “PlusPills”

A Demonstration Open Label Study to Assess the Acceptability and Use of Truvada Pre-exposure Prophylaxis in Healthy, HIV-Uninfected Adolescents, 15-19 Years of Age.

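### The primary safety analysis is not tied to exposure, although adverse events are collected for 52 weeks whether or not the participant is taking PrEP

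*SAP*

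**What the plan says.** The SAP (A. Primary, 3. Primary: Safety) defines the endpoint as "Grades 2, 3, and 4 clinical and laboratory adverse events" and gives the method as "This analysis will be based on descriptive statistics". Protocol Section 10.6 says the same. Neither adds a population, a denominator, an on-treatment window or a breakdown by PrEP use.

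Collection is wide. Protocol Section 8.1 counts adverse events "from the time of enrollment through when s/he terminates from the study", states that "AEs and SAEs will be reported throughout the period of trial follow up", and adds that "All AEs will be captured regardless of the association or otherwise to the study intervention". Each report carries the event date and "the relationship to study intervention, the action taken, the outcome, date resolved, and the severity of the event".

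Exposure varies by design. The Protocol Summary says "Participants will be followed regardless of PrEP usage for a total of 12 months (52 weeks". Section 4.1 keeps those who opt out in follow-up without tablets, and Section 4.3 allows opting out at any time. For the first three months the SAP assumes that use "will be 100% for all 150 participants". Section 7.4 offers no product at week 48, yet Section 7.6 still records adverse events at week 52.

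Elsewhere the plan does use exposure. Total time on PrEP, per participant and for the cohort, belongs to the primary Use endpoint (SAP A.1). The sexual-activity analysis separates on-PrEP from off-PrEP visits (SAP B.2a). HIV incidence is given per 100 person-years with a censoring rule (SAP B.3).

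**The concern.** The objective is the safety of a daily PrEP regimen within a prevention package. With no control arm, the reader needs to know how many events occurred over how much time on drug. The events collected will be a mixture of on-drug and off-drug events, in proportions set by how many participants opt out and when. A plain tabulation of them answers a different question from the objective.

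Because the summary measure and denominator are also unstated, both would be chosen after the opt-out pattern and the events are known. That choice affects not only the size of the reported figure but also the direction in which it departs from the on-drug figure.

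**Working it through.** **Inputs.** 150 enrolled and 52 weeks of follow-up (Protocol Summary); 12-week initial use period (Protocol Summary; SAP A.1); last supply at week 36, used to week 48 (Protocol Section 7.4). The documents give no adverse event rate and no expected opt-out share, so both are assumed below and shown as ranges.

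**The plan's own figure.** The safety section states none. The enrolment figure reproduces: 135/(1 − 0.10) = 150.

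**One participant.** With f = weeks on drug/52:
- stop at week 12: 12/52 = 0.23, so 77% of follow-up is off drug
- stop at week 24: 24/52 = 0.46, 54% off drug
- stop at week 36: 36/52 = 0.69, 31% off drug
- use to week 48: 48/52 = 0.92, 8% off drug

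The value 12/52 is not a strict floor, because opting out before week 12 is allowed.

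**Person-time rate for the cohort.** Assume full follow-up, a share s stopping at week 12, and the rest using PrEP to week 48. Then f = [12s + 48(1 − s)]/52, and on-PrEP person-years = 150f.

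All-follow-up rate = f × r_on + (1 − f) × r_off.

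Subtracting r_off leaves f × (r_on − r_off). The drug-related excess is therefore diluted by 1/f, whatever the rate ratio. The all-follow-up rate as a share of the on-drug rate is [f × RR + (1 − f)]/RR, with RR = r_on/r_off. RR is assumed.

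| Share stopping at week 12 | On-PrEP person-years of 150 | Dilution of excess (1/f) | All-follow-up rate as share of on-drug rate: RR 1.5 | RR 2 | RR 3 |
|---|---|---|---|---|---|
| 0% | 138.5 | 1.08 | 97% | 96% | 95% |
| 10% | 128.1 | 1.17 | 95% | 93% | 90% |
| 20% | 117.7 | 1.27 | 93% | 89% | 86% |
| 50% | 86.5 | 1.73 | 86% | 79% | 72% |
| 100% | 34.6 | 4.33 | 74% | 62% | 49% |

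Example for 20%: f = (0.2 × 12 + 0.8 × 48)/52 = 40.8/52 = 0.785; 150 × 0.785 = 117.7; 1/0.785 = 1.27. At RR = 1 the two rates are equal in every row.

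The 10% and 20% rows borrow the plan's sample-size section, which considers non-uptake and non-use of 5% to 20% with 10% as the design value. Reading those values as shares stopping at week 12 is an assumption. Most cohort time is off drug only if more than (48 − 26)/36 = 61% stop at week 12.

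**Proportion with at least one event.** Take a week-12 stopper with assumed constant rates of 40 per 100 person-years on drug and 20 off.
- All 52 weeks: 1 − exp[−(0.231 × 0.40 + 0.769 × 0.20)] = 21.8%
- On-drug time only: 1 − exp(−0.231 × 0.40) = 8.8%

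With equal rates of 20 per 100 person-years the figures are 18.1% and 4.5%. Off-drug background events therefore raise the proportion even when the drug has no effect. This is the opposite direction to the person-time rate.

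**The case against.** A reader might infer that the SAP pools all follow-up, and that it therefore makes the drug look up to 4.3 times safer than it is. The documents do not support that. The safety sentence mentions neither pooling nor a rate; the passages on follow-up and on event recording govern collection, not tabulation. Understatement needs both a person-time rate over all follow-up and a higher event rate on drug than off. The 4.3-fold figure applies only to the drug-related excess, and only if all 150 stop at week 12. At the plan's own 10% to 20% non-use, the dilution is modest.

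Four further points deserve weight.
- Descriptive statistics could include a table by relatedness and exposure. Each report carries date and relationship, and time on PrEP will be reported. The safety team reviews data about monthly and the monitoring committee about every three months. This is true, but none of it specifies the final table.
- The objective covers PrEP as part of a package, so a summary over all follow-up is legitimate. It should stay, as a second table.
- Off-PrEP time is not the only internal reference, since laboratory values are taken at screening. It is also a weak one: opting out is self-selected (Protocol Section 2.5 itself expects differences), adverse events can trigger holds and discontinuation (Sections 9.1 and 9.7), and visits are 4-weekly to week 12 but 12-weekly afterwards, so ascertainment changes with exposure. This limits interpretation of the contrast. It does not remove the need for an on-PrEP rate.
- Exposure dates will be imprecise. Participants may stop on their own between visits (Section 7.10.4), and no section says explicitly that hold dates are recorded. This stands as a limitation.

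**Conclusion.** The point holds as a gap in specification. For a primary endpoint, the plan does not define the safety denominator or the exposed period, in a design where a participant may be off drug for 77% of follow-up or more. An all-follow-up summary would not describe safety on PrEP.

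The likely effect on a person-time rate is small to moderate: a 1.08- to 1.27-fold dilution of any excess if up to 20% stop at week 12, 1.7-fold if half stop, and 4.3-fold only at the extreme. These figures assume full follow-up, stopping at week 12 or use to week 48, and constant rates on and off drug. A proportion with at least one event moves the other way. The documents do not determine which of these would be reported, so no single corrected figure can be given.

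This is more than missing detail, because the plan already measures exposure and uses on/off phases for a secondary endpoint, but does not apply either to safety.

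**What to change.** In SAP A.3 (and Protocol Section 10.6):

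1. Define the safety population, and one attribution window after the last supply or stop, before the data are examined.
2. Report Grade 2 to 4 events per person-year with exact 95% confidence intervals for on-PrEP time, and separately for off-PrEP time. Use the on-PrEP time derived for the Use endpoint, and state which version is meant: the Protocol Summary bases it on self-report, while Section 4.2 refers to drug levels.
3. Add the number and proportion of participants with at least one event, by grade and relatedness.
4. Keep the all-follow-up table as a second summary.
5. Label the on/off contrast descriptive and not causal, giving the reasons: self-selected opt-out, event-triggered holds and the change in visit frequency.
6. Optionally, add a sensitivity table with exposure defined by drug level. It is limited, because after week 12 there is only about one sample per 12-week interval, taken in those on PrEP.

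The Protocol Summary schedules product for 52 weeks, whereas Section 7.4 offers none at week 48. These must be reconciled because they change exposed time.

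The cost is slightly more programming. The inputs are largely planned already: event dates, dispensing and returns, and continue/stop decisions. Stop and hold dates between visits will be approximate, so the SAP should state how they are assigned.

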across sites. The most commonly noted reasons for missing medications included missed or late clinic visits and pregnancy, for which participants were taken off the study drug. Preliminary results from the Bangkok PrEP study show participant adherence rates of 92% in the week prior to study visit (Choopanya et al., 2013). According to investigators in the Partners PrEP study, participants achieved adherence levels of 99% during an average four-month period during the two-year study (Haberer et al., 2011). However, both iPrEx, CAPRISA 004 and VOICE data demonstrate the bias of self-report in over-reporting adherence. In the iPrEx trial, non-adherence to study medication was strongly associated with infection risk with only 9% of those newly infected having detectable drug in their blood (Grant et al., 2010), despite high levels of self-reported adherence. Thus, optimizing adherence and its measurement is critical for interpretation of efficacy data and implementation planning (Buchbinder & Liu, 2011). Recent thinking has described 3 phases to adherence: initial uptake, persistence or continued usage and finally quality of the adherence to sustained use in terms of numbers of prescribed doses taken (Bangsberg DR, et al 2001). This proposal aims to investigate all 3 aspects of adherence: uptake, persistent use and quality of adherence. Use of drug levels real time is explored as a way to enhance the ongoing quality of medication adherence over time.

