The DTHF protocol and research teams hypothesize that oral once daily PrEP (TDF/FTC) will be acceptable and utilized safely by healthy adolescents, between the ages of 15-19 years.

SAMPLE SIZE CONSIDERATIONS

The sample size calculation is based on the ability to detect the measure the primary

CHAMPS: Choices For Adolescent Prevention Methods for SOUTH AFRICA

Pilot study B: “PlusPills”

A Demonstration Open Label Study to Assess the Acceptability and Use of Truvada Pre-exposure Prophylaxis in Healthy, HIV-Uninfected Adolescents, 15-19 Years of Age.

objectives (acceptability and use) in the participant population. The table below shows the precision (as 95% confidence limits) provided by various sample sizes in detecting the occurrence of acceptability endpoints (with a frequency non- uptake and use varying from 5%-20%).

Acceptability will be measured by proportion of youth who take up PrEP and remain on PrEP as part of a comprehensive prevention package. Also they will complete an acceptability questionnaire.

	Precision *		
Frequency	n=100	n=135	n=170
5%	1.6; 11.2	2.1; 10.4	2.4; 9.8
10%	4.9; 17.6	5.7; 16.8	6.4; 16.2
15%	8.6; 23.5	9.9; 22.8	10.7; 22.2
20%	12.7; 29.1	14.2; 28.6	15.3; 28.1

* Asymptotic (exact) binomial 95% confidence limits

Based on these calculations, we anticipate that 135 participants, rounded up to 150 participants to account for premature censoring (due to loss to follow-up and/or withdrawal of consent, estimated at maximum 10%) will be required to detect non-acceptability endpoints that occur in 10% of subjects with approximately 5% precision.

DATA AND SAFETY MONITORING AND REVIEW

In addition to the informal safety monitoring done by the Site Investigator and study clinician, DTHF will convene an independent Protocol Safety Review Team (PSRT). The roles of the PSRT are:

CHAMPS: Choices For Adolescent Prevention Methods for SOUTH AFRICA

Pilot study B: “PlusPills”

A Demonstration Open Label Study to Assess the Acceptability and Use of Truvada Pre-exposure Prophylaxis in Healthy, HIV-Uninfected Adolescents, 15-19 Years of Age.

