participant. In analysis, we will first use graphical approaches to display the proportions of participants reporting binary sexual risk behaviours (or means of continuous measures) at each study visit over the 12-month period. Following this, we will use repeated measures methods (as described above) for both binary and continuous dependent variables, with PrEP access treated as a binary variable distinguishing visits in on vs. off PrEP phases; in the first instance, these models will not include other covariates.

2b. Proportion of scheduled HIV testing appointments that are missed, in relation to individual characteristics (age, sex, number of partners, use of other prevention methods) and the characteristics of the product.

Analysis:

“Missed appointments” will be defined as participants being >7 days late for a visit scheduled on a 28-day cycle. This measure will be analysed as a binary variable following the repeated measures approaches described above.

3. Secondary: HIV Incidence

HIV infection, as measured by seroconversion of study participants during the approximate 12 months of follow-up

Analysis:

The incidence of HIV will be described using person-time (rates per 100 person years of observation) and product-limit (survival proportion) approaches. For both methods, the date of seroconversion will be the midpoint of the interval between the last negative and first positive HIV test. For participants lost to follow-up, the date of censoring will be one day after the last visit attended.

C. Exploratory Endpoints:

1. Exploratory: Dried Blood Spot/plasma biofeedback

Correlation of self reported adherence and presence of drug levels in participants who are tested using plasma drug levels or DBS and received results compared to participants who are tested using plasma/DBS but do not receive biofeedback of results.

CHAMPS: Choices For Adolescent Prevention Methods for SOUTH AFRICA

Pilot study B: “PlusPills”

A Demonstration Open Label Study to Assess the Acceptability and Use of Truvada Pre-exposure Prophylaxis in Healthy, HIV-Uninfected Adolescents, 15-19 Years of Age.

Analysis:

These data will be described as proportions at each study visit; while we will calculate differences in proportions attending between participant who do and do not receive biofeedback results, no formal statistical tests will be used for this exploratory endpoint.

2.Exploratory: Sexual behaviour by coital diaries

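### The adherence analysis uses drug levels only as a yes/no measure, so its continuous models rest on self-report and pill counts, and the listed drug-level correlation is narrowed to presence of drug

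*SAP*

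**What the plan says.** SAP B.1 (Secondary: Adherence), repeated in protocol 10.6, names three adherence measures: self-report, pill count and drug level. It defines two binary metrics, perfect and effective adherence, and then restricts the third measure: "Note that drug levels will be used in analyses of effective adherence only". For drug levels, effective adherence means a therapeutic level; no numeric threshold is given. The binary metrics are to be analysed "as well as continuous measures of the proportion of PrEP doses taken", at each visit and over the whole study, with mixed models for the repeated measures.

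The endpoint lists (protocol 4.2 and 10.2, and the SAP's exploratory endpoints) include the correlation of self-reported adherence with drug levels at each visit, per participant and overall. None of these lists says that the level is dichotomised. The matching analysis text in SAP C.1 reads "Correlation of self reported adherence and presence of drug levels in participants", and the data are to be described as proportions without formal tests.

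On the measures themselves, protocol 2.6.7 says that earlier PrEP trial "data demonstrate the bias of self-report in over-reporting adherence".

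**The concern.** The study's rationale (protocol 2.5) is that women in two earlier trials reported high use while their drug levels showed very poor use. Protocol 2.6.7 then makes the quality of adherence, a graded quantity, one of the study's aims. Under B.1, however, any graded trend or predictor model can be fitted only to self-report and pill counts.

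The levels are plainly available as numbers. Under protocol 2.5, participants who ask are told their level, and a safety team looks for unusually high values. As a yes/no measure, a level just above the cut and one far above it count the same. A decline that stays above the cut cannot be seen, nor can a difference among users who all fall below it.

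The correlation endpoint has a further problem. A binary variable that never changes within a person has no variance, so for that person the correlation cannot be computed.

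**Working it through.** **1. The text, side by side.**

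| Item | Self-report | Pill count | Drug level |
|---|---|---|---|
| Perfect adherence (binary), B.1 | yes | yes | excluded |
| Effective adherence (binary), B.1 | yes | yes | yes |
| Share of doses taken (continuous), B.1 | yes | yes | not supplied |
| Correlation endpoint, as listed | graded scale | – | level, no cut stated |
| Correlation endpoint, as analysed in C.1 | graded | – | presence only |

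This step needs no assumption.

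**2. The per-participant correlation.** Protocol 7.8 schedules at most seven samples per person (weeks 4, 8, 12, 24, 36, 48 and 52), the later ones only in those on product. The correlation is r = cov(x, y)/(SD_x × SD_y). If presence is always 1 or always 0, SD_y = 0 and r is undefined. Self-report is graded on a visual scale (protocol 4.1), so a level-against-scale comparison is available.

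**3. The plan's own sample-size figure.** "we anticipate that 135 participants, rounded up to 150 participants to account for premature censoring": 135/(1 − 0.10) = 150, which reproduces. Exact 95% limits for 14/135 are 5.8 and 16.8; the plan prints 5.7 and 16.8. The stated aim is "required to detect non-acceptability endpoints that occur in 10% of subjects with approximately 5% precision". This is a precision target, so the plan sets no power for any drug-level comparison.

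**4. What dichotomising could cost.** From the documents: "all statistical tests will be 2-sided using an alpha of 0.05"; 135 evaluable; about one boy to two girls (protocol 4.1; section 4.3 gives 30:45 per site). Assumed, because the documents give none of these: the distribution of levels, the size of the difference and the position of the cut.

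*Normal shift, closed form.* Groups of 45 and 90, difference d = 0.5 SD in log level.
- Full scale: d√(n₁n₂/N) = 0.5 × √(45 × 90/135) = 0.5 × √30 = 2.739. Power = Φ(2.739 − 1.960) = Φ(0.779) = 78.2%.
- Cut at the pooled median: the shares above the cut are 37.0% and 56.6%, a difference of 0.197. Null SE = √(0.25/30) = 0.0913. Alternative SE = √(0.370 × 0.630/45 + 0.566 × 0.434/90) = 0.0889. Power = Φ((0.197 − 1.960 × 0.0913)/0.0889) ≈ 57.9%.
- Gain from the full scale: 20.3 points. With 30% above the cut, binary power is 49.6% and the gain is 28.6 points.

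*Normal shift, simulation.* Rank-sum test against a test of proportions; shifts of 0.4 to 0.6 SD in either direction; 0 to 50% of values below quantification; cut at the 30th to 80th percentile and never below that limit.
- n=135 (90 and 45): full scale ahead by about 7 to 38 points.
- n=60 (40 and 20, an assumed number of later users): ahead by about 1 to 30 points.

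*Groups differ only in the share taking drug*, with levels among takers identically distributed, n=135, cut at detectability:
- 70% against 45%: pooled share (90 × 0.70 + 45 × 0.45)/135 = 0.617. Null SE = √(0.617 × 0.383/30) = 0.0888. Alternative SE = √(0.21/90 + 0.2475/45) = 0.0885. Binary power = Φ((0.25 − 1.960 × 0.0888)/0.0885) = Φ(0.86) ≈ 80%. Simulation gives about 82% for the yes/no test and 70% for rank-sum.
- 80% against 60%: about 70% for the yes/no test and 46% for rank-sum.

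The sign of the difference therefore depends on how levels are distributed.

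**The case against.** Four points weigh against making much of this.

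- **The cut has a reason.** Effective adherence is tied to protection seen in efficacy trials. That stands, and it justifies reporting the cut. It does not explain why other uses of the level are excluded.
- **Little formal testing is at stake.** The sample size rests on precision, B.1 is largely descriptive, its predictor models are labelled exploratory with limited power, and C.1 has no tests. This stands, and it is why the loss is better described as information than as power.
- **Yes/no can be the better scale.** Protocol 2.5 expects a mixture of users and non-users, and for that pattern the binary test can win. This stands, and it rules out replacing the binary analysis.
- **A full-scale level has limits of its own.** Protocol 2.5 says that the real-time assay is non-cellular and that such levels show recent use. Some of the variation will reflect time since the last dose. Someone whose values are all below quantification still has no usable individual correlation. Both stand as caveats.

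A reader might also infer that drug levels appear only as yes/no throughout the plan, or that the protocol calls both other measures biased. The documents support neither. The listed correlation endpoint carries no cut, and section 2.6.7 speaks of self-report and says nothing against pill counts, which are a separate, non-biological check.

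**Conclusion.** The concern holds as a gap in the adherence analysis and as a mismatch between a listed endpoint and its analysis. Both follow from the text alone. Drug level, the only biological adherence measure, is absent from every continuous adherence model in B.1, and C.1 reduces the listed correlation to presence.

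It is tempting to go further and say that the cut costs a known amount of power. The documents give no distribution, effect size or threshold, so they cannot support that. Under a normal shift the full scale gains about 7 to 38 points at n=135 and 1 to 30 at n=60; if groups differ only in the share taking drug, the yes/no test can be 10 to 25 points stronger. The secure claim is that a full-scale analysis keeps information the plan now discards, from samples already scheduled. It is worth making the change, but no confirmatory conclusion depends on it.

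**What to change.** 1. In SAP B.1 and protocol 10.6, replace the restricting sentence with: *Drug levels will be analysed (i) as effective adherence (binary) and (ii) on the full concentration scale at each visit (log scale with values below the quantification limit treated as left-censored, or rank-based), separately by matrix and analyte.*
2. Report (ii) alongside (i), not in place of it, in the descriptive, predictor and repeated-measures analyses.
3. In SAP C.1 and the matching text of protocol 10.6, correlate the measured level with the visual adherence scale, per participant and overall, as the endpoint list has it. Report how many participants have no usable individual correlation.
4. State beside the results that non-cellular levels mainly reflect recent dosing.

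The cost is a wording change in two documents, one more exploratory model on data already planned, a rule for values below quantification, and separate handling of plasma and dried blood spot results. No extra visits or samples are needed.
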